32.1.1 Population PK analysis

A population PK analysis of MOR00208 will be conducted. The planned meta-analysis will encompass PK data from study MOR208C203 and other clinical trials with MOR00208. The analysis will provide an understanding of the population PK of MOR00208 and determine the influence of intrinsic and extrinsic factors (such as but not limited to age, gender, race, level of hepatic or renal function and presence of anti-drug antibodies) that may influence PK variability. Details of the intended population PK analysis will be described in a separate population PK protocol and the results will be described in a separate population PK study report.

10.10 Secondary objective 10

To make a preliminary evaluation of ORR, DCR, DoR, PFS, OS, TTP and TTNT in patients treated with a combination of LEN plus MOR00208 in cohorts with a “low risk”, “low- intermediate”, “high-intermediate” and “high” International Prognostic Index (IPI).

10.10.1 Endpoint

ORR, DCR, DoR, PFS, OS, TTP, and TTNT stratified by:

- four risk categories: “low risk”, “low-intermediate risk”, “high-intermediate risk” and “high risk”.
- two risk categories: “low risk” and “low-intermediate risk” vs. “high-intermediate risk” and “high risk”.

10.10.2 Main analysis

- The main analyses are described above in the respective sections addressing ORR, DCR, DoR, PFS, OS, TTP, and TTNT (see Sections 9.2, 10.1.3, 10.3.4, 10.2.5, 10.4.4, 10.5.3, 10.6.3).
- For the analysis comprising two risk categories: An estimate of the hazard ratio and corresponding 95% CI will be calculated for PFS and OS analyses using a Cox proportional hazard model with only one covariate in the model.

10.10.3 Sensitivity analyses

The main analyses as described in Section 10.10.2 will be conducted based on the INV response assessment (see sections 9.3, 10.1.4, 10.3.5, 10.2.6, 10.4.5, and 10.5.4).

10.11 Secondary objective 11

10.11.1 Objective

To compare each patient’s TTP on LEN plus MOR00208 with the TTP of their most recent prior therapy.

10.11.2 End point and main analysis

End point analyses are described in detail above in section 10.5.3.

10.12 Secondary objective 12

10.12.1 Objective

To correlate efficacy parameters with certain biomarkers (e.g. peripheral NK cell count, constitutional FcγRIIIa and FcγRIIIa polymorphism status).

10.12.2 Endpoint

PFS, DoR, ORR, OS will be analyzed in the following subgroups:

- FcγRIIIa affinity (high affinity: FCGR3A-158V homozygosity vs. low affinity: FCGR3A-158F homozygosity, or FCGR3A-158F/V heterozygosity).
- FcγRIIIa affinity (high affinity: FCGR2A-131H homozygosity vs. low affinity: FCGR2A-131R homozygosity, or FCGR2A-131H/R heterozygosity).
- Peripheral NK cell numbers at baseline (< median of NK cell numbers/μl vs. >= median of NK cell numbers/μl).
- Cell of origin determined by immuno-histochemistry (IHC) (i.e., central pathology) assessment: germinal center B cell (GCB) phenotype vs. non-GCB phenotype.
- Cell of origin determined by gene expression profiling (GEP): GCB phenotype vs. activated B cell (ABC) phenotype vs. unclassified phenotype.

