10.4 General Statistical Methods

Tabulation of summary statistics, graphical presentations, and statistical analyses will be performed using appropriate statistical software. Continuous, quantitative variable summaries

will include the number of patients (N) (with non-missing values/valid cases), mean, standard deviation, minimum, 25th quartile, median, 75th quartile and maximum, except for pharmacokinetic metrics, where additional statistics may be used.

Categorical, qualitative variable summaries will include the frequency and percentage of patients/entries, who/which are in the particular category.

The assumed overall type I error rate/significance level for the primary and secondary efficacy parameters is 5%, two-sided. Two-sided confidence limits will be evaluated at 95%, p-values from inferential tests comparing specific patient cohorts/patient subgroups will be compared to 5%.

Missing values will not be substituted by estimated values. All statistical evaluations will be based on valid cases except for procedures described for calculating response rates or in case of censoring within the Kaplan-Meier methodology. In the case of incomplete start or stop dates of AEs or concomitant medication appropriate conservative imputation methods will be specified in the Statistical Analysis Plan (SAP).

Baseline values will be defined as the last pre-administration observation used for calculating post-administration changes from baseline.

All data obtained and entered into the database will be provided in separate data listings showing individual patient values. A SAP detailing the statistical analyses and possible deviations from the protocol will be prepared before hard lock of database.

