5.3 Determination of sample size

Approximately 80 patients with R-R DLBCL who meet all of the inclusion criteria and have none of the exclusion criteria will be enrolled into the study. The study will be performed with an interim stop for the evaluation of the safety of the LEN dosage. No adjustment of sample size or adaptation of efficacy evaluations will be made at this point. As the primary purpose of this study is to evaluate the clinical efficacy of 25 mg daily oral LEN combined with 12 mg/kg MOR00208 administered by IV infusion in patients with R-R DLBCL, no formal statistical hypothesis testing will be performed.

**STATISTICAL ANALYSIS PLAN**MorphoSys AG
MOR208C203

For the determination of a suitable sample size, it is assumed that the combination treatment could improve the ORR of LEN from a value of 20% (under monotherapy) to 35% (under combination therapy). Applying an exact binomial test with a two-sided significance level of 5% and a power of 85% the estimated sample size is 73 patients (calculation performed by nQuery Advisor® 7.0). According to this scenario an observed ORR of 32% would lead to the conclusion that the outcome is statistically superior to outcomes observed previously for the monotherapy. Assuming a drop-out rate of 10%, a total sample size of about 80 patients is estimated.

The sample size determination has been conducted using various possible monotherapy and combination effect ORR rates and various power assumptions. Literature evaluation of study results concerning the ORR rates of LEN or comparable products (as mono- or combination therapy) as well as study results for MOR00208 ongoing studies were used to justify assumptions on response rates (Witzig et al., 2011; Wang et al., 2013).

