10.12.3 Main analysis

The following analyses will be conducted on the FAS:

- The main analyses pertaining to the biomarker subgroup analyses are being described in the respective sections above addressing ORR, PFS, DoR, and OS (Sections 9.2, 10.1.3, 10.2.5, 10.3.4, and 10.4.4).
- PFS, DoR and OS will be compared between subgroups by a log-rank test.
- For PFS and OS analyses, the estimate of the hazard ratio and corresponding 95% CI will be calculated using a Cox proportional hazards model with only one covariate (i.e., the biomarker in question) in the model.

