16.5.8 NK cell numbers at baseline

In analogy to the subgroup analysis specified in Section 10.12 the NK cell categories are additionally defined using a cut-off of 100 NK cells/ μ l (<100 cells/ μ l vs. \geq 100 cells/ μ l). The following efficacy analyses will be conducted based on the FAS:

- PFS (based on IRC only)
- OS
- ORR (based on IRC only)
- DoR (based on IRC only)

Kaplan-Meier curves will be produced for time-to-event endpoints.

Baseline characteristics in the NK count subgroups defined by the cut-off of 100 NK cells/ μ l will be tabulated as described in Section 8.5.

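### Objective 12 asks for a correlation with NK cell count, but this SAP's only inferential analysis cuts the count into two groups; a continuous model on the same data would use more of the information

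*SAP*

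**What the plan says.** SAP 10.12.1 states the objective: "To correlate efficacy parameters with certain biomarkers (e.g. peripheral NK cell count" is one of its named examples.

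SAP 10.12.2 lists the subgroups in which PFS, DoR, ORR and OS are analysed. For NK count the lower group is "Peripheral NK cell numbers at baseline (< median of NK cell numbers" per µl, and the upper group is everyone at or above the median. SAP Table 1 gives the same split.

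SAP 10.12.3 sets the analysis: "PFS, DoR and OS will be compared between subgroups by a log-rank test". For PFS and OS it adds a hazard ratio "using a Cox proportional hazards model with only one covariate (i.e., the biomarker in question) in the model". For ORR it refers back to SAP 9.2, which gives rates with Clopper-Pearson limits and no measure of association.

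In Addendum 1, SAP 16.5.8 says that "the NK cell categories are additionally defined using a cut-off of 100 NK cells" per µl. It gives no reason for that value. The forest plots in 16.5.6 use the 10.12 groups, hence the median. Those in 20.6.2, 20.8.2, 20.8.3 and 23.1.2 use 100 cells/µl.

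The undivided count appears in two places, both descriptive: the summaries in SAP 12, and the by-visit summaries for responders and non-responders in Addendum 5 (20.1).

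On error rates, Protocol 10.4 says "The assumed overall type I error rate/significance level for the primary and secondary efficacy parameters is 5%, two-sided", and that "p-values from inferential tests comparing specific patient cohorts/patient subgroups will be compared to 5" per cent.

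**The concern.** A correlation with a count asks how outcome changes along the scale of that count. The planned test asks only whether patients above the median differ from those below it. It treats a patient just above the median like the patient with the highest count, and unlike the patient just below. With about 80 patients there is little information to spare.

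NK count also bears on the mechanism. The protocol's rationale (section 2) is that LEN enhances the NK-cell-mediated ADCC exerted by MOR00208. A relation missed here would be a relation the trial was partly set up to look for.

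Two further consequences follow. A median cut moves with the sample, so its hazard ratio does not carry over to another trial; a fixed cut at 100 cells/µl does not share that defect. And with two cuts and no stated lead, the plan does not settle in advance which NK result answers the objective.

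**Working it through.** **Inputs from the documents.** Sample size: "Approximately 80 patients with R-R DLBCL who meet all of the inclusion criteria" (SAP 5.3). Significance level: 5%, two-sided (Protocol 10.4). The plan gives no power, event count, effect size, NK distribution or share of patients below 100 cells/µl for objective 12, so there is no planned figure to reproduce. The sample size rests on ORR alone.

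**Assumptions.** Log NK count is roughly normal and its effect on the log hazard is linear. Events D: 30 to 60. Hazard ratio (HR) per SD: 1.2 to 1.8.

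**Formulae.** For a Cox score test on a standardised continuous covariate, power = Φ(√D × |ln HR| − 1.96). A cut with share p below it keeps the fraction e(p) = φ(z_p)² / [p(1 − p)] of the information, so D is replaced by D × e(p). At the median, e = (1/2π)/0.25 = 2/π = 0.637. Thus 48 events analysed by median split are worth 48 × 0.637 ≈ 31 analysed on the full scale.

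**Worked case: 50 events, HR 1.5 per SD.**
- Continuous: √50 × 0.4055 = 2.867; Φ(2.867 − 1.96) = 82%.
- Median split: 2.867 × √0.637 = 2.288; Φ(2.288 − 1.96) = 63%.
- Cross-check: the halves differ on average by 2√(2/π) = 1.596 SD, so the between-group HR is 1.5^1.596 ≈ 1.91. Schoenfeld's formula with 50 events again gives 63%.

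**By formula, continuous against median split:**

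| Events | HR 1.2 | HR 1.3 | HR 1.5 | HR 1.8 |
|---|---|---|---|---|
| 30 | 17% / 12% | 30% / 21% | 60% / 43% | 90% / 73% |
| 40 | 21% / 15% | 38% / 26% | 73% / 53% | 96% / 84% |
| 50 | 25% / 18% | 46% / 32% | 82% / 63% | 99% / 91% |
| 60 | 29% / 20% | 53% / 37% | 88% / 71% | 99.5% / 95% |

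**By simulation** (80 patients, 48 events, 3,000 trials per setting): HR 1.3, 44% against 29%; 1.4, 63% against 43%; 1.5, 77% against 57%; 1.6, 88% against 69%; 1.8, 97% against 85%. The loss is 12 to 20 points. With 36 events it was 13 to 23 points, and with 60 events 8 to 21.

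**The 100 cells/µl cut.** Its loss depends on the unknown split. By formula, e = 0.576 at 30/70 and 0.490 at 20/80, so 80% continuous power falls to 57% and 50%. In simulation the losses were 8 to 20 points at 30/70 and 10 to 23 at 20/80.

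**If the shape assumption fails.** With a simulated step exactly at the median and about 50 events, the split had 54% power and the linear term 43%.

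**The case against.** The strongest objection is that the rest of the biomarker plan is unseen. SAP 10.12.4 announces a separate biomarker-specific SAP, and 5.4.3 foresees further exploratory work on biomarkers and response. A reader might infer that no continuous NK analysis was planned anywhere. The documents do not support that; the point covers this SAP only. Within it, 10.12.3 is the main analysis of objective 12, and that part stands.

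Second, no stated standard is breached. Objective 12 has no power target, the protocol labels NK counting an exploratory assay, and SAP Table 1 defines the endpoint as stratification, so the SAP is consistent with itself. This is fair: the point is an improvement, not a contradiction.

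Third, the power loss is conditional. It is only 5 to 9 points at HR 1.2 per SD with 30 to 60 events, about 4 points at 60 events and HR 1.8, and reversed by a step at the median. It should not be read as a known property of this trial. However, the documents claim no threshold, and a single step cannot lie at two different cuts.

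Other tempting readings go too far:
- That the full-scale count is never set against response: SAP 20.1 does so, descriptively.
- That 100 cells/µl was chosen because it looked better: nothing shows this. Both cuts are written down, the second is called additional, and 16.5.8 names no log-rank or Cox test itself; it says only that it works by analogy with 10.12.
- That every patient has a count, or that NK count is the key predictive biomarker: neither is stated, and a single-arm trial cannot separate predictive from prognostic effects under any model.

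**Conclusion.** The concern holds for this SAP. Its stated objective is a correlation, its only inferential NK analysis is a comparison of two groups, and ORR has no measure of association with NK count at all.

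Under a roughly normal log count and a log-linear effect, the median split gives up 36% of the information. Over the assumed 30 to 60 events and HR per SD of 1.3 to 1.8, the cost is about 8 to 23 points of power in simulation, mostly 10 to 20. It is smaller where power is very low or near 100%, and absent if the true effect is a step at the cut. The loss from the 100 cells/µl cut cannot be fixed without the share of patients below it.

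The consequence is limited. The objective is secondary and unpowered, and the primary ORR conclusion does not depend on it. The change is worth making because it answers the objective better at little cost.

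**What to change.** In SAP 10.12.3, add as the lead NK analysis a Cox model for PFS and OS and a logistic model for ORR, with log2 baseline NK count as a continuous covariate. Report the hazard or odds ratio per doubling with its 95% CI, and state how a zero count is handled. Add a restricted cubic spline with three knots as a shape check for PFS and OS. Treat DoR as descriptive support: it uses responders only, about 0.35 × 80 = 28 at the design ORR. Keep the median and 100 cells/µl splits for Kaplan-Meier and forest-plot display, without p-values. If the biomarker SAP already holds such a model, cross-refer to it.

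The SAP has reached Addendum 8, with 48-month rates. If NK results are already known, label the new analysis supplementary and post hoc.

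The cost is SAP wording and a few lines of code on data already collected. The downside is the log-linearity assumption, which the spline checks only roughly at this sample size.

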10.12.3 Main analysis

The following analyses will be conducted on the FAS:

- The main analyses pertaining to the biomarker subgroup analyses are being described in the respective sections above addressing ORR, PFS, DoR, and OS (Sections 9.2, 10.1.3, 10.2.5, 10.3.4, and 10.4.4).
- PFS, DoR and OS will be compared between subgroups by a log-rank test.
- For PFS and OS analyses, the estimate of the hazard ratio and corresponding 95% CI will be calculated using a Cox proportional hazards model with only one covariate (i.e., the biomarker in question) in the model.

10.12.4 Sensitivity analyses

The main analysis as described in Section 10.12.3 will be conducted based on the INV response assessment using the FAS.

A comprehensive analysis of all biomarker assessments will be described in a separate biomarker-specific Statistical Analysis Plan, and summarized in a separate report.

11. EXPLORATORY EFFICACY ANALYSES

11.1 Time to response and time to complete response

The time to response will be calculated and tabulated for patients achieving response (PR of CR). The time to response [months] is defined as follows:

$((\text{date of assessment of first documented response of (CR or PR)}) - (\text{date of first administration of any study drug}) + 1) / 30.4375$.

Moreover, the time to complete response [months] will be calculated and tabulated for patients achieving complete response. The time to complete response is defined as follows:

$((\text{date of assessment of first documented complete response (CR)}) - (\text{date of first administration of any study drug}) + 1) / 30.4375$.

The time to response will be calculated using the FAS for both the INV and IRC assessment.

11.2 PET-Confirmed Complete Responses

Number (%) of patients with a PET-confirmed CR at any point in time will be presented for the IRC response assessment. The device used for imaging for a particular Visit can be found on the 'Lymphoma Tumour Assessment' eCRF page. The following devices will be considered as PET modality:

- PET/CT
- PET/MRI
- PET

A separate listing will show those patients who reached a PET-confirmed CR (SAF).

11.3 Tumor shrinkage over time: Assessment of indicator lesions

Data on lesion size will be presented by descriptive statistics and individual data listings (for the SAF). The sum of the product of the longest perpendicular diameters (SPD) reflecting the lesion area will be used for the analysis (based on the IRC assessment). Data will be presented separately for the two central reviewers.

The area of indicator lesions will be examined as follows:

1. Analysis across all points in time:

- Absolute values and both absolute and the individual relative changes (from baseline) for each patient will be summarized for each visit.

-
- A graph showing the individual relative changes over time will be generated separately for both central readers. The best overall response of each individual will be indicated by colour coding (CR, PR, SD, PD, NE=not evaluable).

2. Analysis comparing baseline and nadir:

- The area of indicator lesions will be reported at baseline and at the nadir. The absolute value and both the absolute and relative difference between baseline and nadir will be reported.
- A “waterfall plot” indicating the best change (%) for indicator lesions will be generated separately for both central readers.

3. Correlation between radiologists.

The SPD as determined by radiologist 1 at screening and nadir will be correlated with the SPD at screening and nadir as determined by radiologist 2. The Pearson Correlation Coefficient will be derived for both assessments, i.e., at screening and nadir.

Listings showing individual lesion sizes over time will be produced.

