9.4 Concordance between IRC and investigator (INV) assessment

The concordance rate in terms of response assessment represents the agreement in the best overall outcome (CR, PR, SD, PD, Not Evaluable, and Not Available) in tumour response assessments between the IRC and INV assessment. The concordance rate is the number of patients that are concordant over the total number of patients assessed, and will be calculated across all response categories. A contingency table will be generated. The concordance rate is calculated by adding the diagonal counts and dividing by the total number of patients assessed. Moreover, the agreement (%) of the INV assessment by the IRC in terms of best ORR will be calculated (i.e., the proportion of patients with a best response of CR or PR by investigator assessment that have a confirmed best response of CR or PR by the IRC assessment).

Patients who have been evaluated by investigator assessment, but not by central review assessment will be excluded from the concordance analysis.

The proportion (%) of patients who had at least one central review among the total number of patients who underwent at least one INV assessment will be calculated. Moreover, the proportion (%) of the total number of central reviews among the total number of INV assessments will be derived (i.e., the total number of central reviews across all visits and all patients divided with the total number of investigator response assessments across all visits and all patients multiplied by 100). The analysis will be conducted using the FAS.

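### Pearson's r, the only paired comparison planned between the two central radiologists' lesion areas, cannot show systematic reader disagreement, and percent change is never compared between readers

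*SAP*

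**What the plan says.** SAP 11.3 sits among the exploratory efficacy analyses and describes indicator-lesion area by central review. "Data will be presented separately for the two central reviewers". For each reader the section plans visit-level summaries ("Absolute values and both absolute and the individual relative changes (from baseline) for each patient will be summarized for each visit"), a comparison of baseline with nadir, graphs of relative change over time, and a waterfall plot of best percent change. It adds that "Listings showing individual lesion sizes over time will be produced".

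Item 3, titled "Correlation between radiologists", is the only place where the two readers are paired: "The SPD as determined by radiologist 1 at screening and nadir will be correlated with the SPD at screening and nadir" found by the second radiologist. The statistic is fixed in the next sentence: "The Pearson Correlation Coefficient will be derived for both assessments, i.e., at screening and nadir". No threshold or interpretation is given.

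The other concordance analyses of tumour assessment do not pair the two readers. SAP 9.4 sets central review against the investigator ("The concordance rate in terms of response assessment represents the agreement in the best overall outcome"), and 10.2.7 does the same for PFS events.

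**The concern.** When two people measure the same lesions, the useful question is how far apart their measurements are. Pearson's r asks something else: whether patients with larger areas on one reading also have larger areas on the other. A reader who consistently draws larger boundaries, or consistently includes more tissue, leaves r where it was.

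The section is about shrinkage, yet item 3 correlates only absolute areas at two time points. Reader differences in percent change, the quantity plotted for each reader, get no paired analysis. At stake is whether the report's exploratory lesion data can be read as reproducible between readers. The efficacy conclusions of the trial do not depend on it.

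**Working it through.** The SAP states no figure for reader correlation or agreement, so there is none to reproduce.

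**Inputs.** From the documents: the statistic, the variable and the time points (SAP 11.3), and a planned size of about 80 (SAP 5.3: "Approximately 80 patients with R-R DLBCL who meet all of the inclusion criteria"). Assumed, because the documents give none of them: lognormal SPD with median 25 cm², between-patient log-SD (s_b) of 0.6 to 1.2, random error per reader on the log scale (s_e) of 0 to 0.4, and a multiplier k on the second reader.

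**1. Invariance, with no assumption needed.** For any k > 0 and any constant c, cov(X, kY + c) = k·cov(X, Y) and SD(kY + c) = k·SD(Y). The k cancels and c drops out, so corr(X, kY + c) = corr(X, Y).

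**2. One fixed dataset** (n = 80, s_b = 0.8, s_e = 0.15), with Lin's coefficient CCC = 2·cov / [var₁ + var₂ + (mean₁ − mean₂)²]:

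| Change to reader 2 | Pearson r | CCC |
|---|---|---|
| × 1 | 0.951 | 0.950 |
| × 1.5 | 0.951 | 0.796 |
| × 2 | 0.951 | 0.608 |
| × 3 | 0.951 | 0.384 |
| + 10 cm² | 0.951 | 0.918 |
| + 25 cm² | 0.951 | 0.774 |

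**3. What sets the level of r.** Median r at k = 2 over 1000 simulated datasets per cell (k = 1 gives essentially the same values):

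| s_b | s_e = 0 | 0.1 | 0.15 | 0.2 | 0.3 | 0.4 |
|---|---|---|---|---|---|---|
| 0.6 | 1.00 | 0.97 | 0.93 | 0.88 | 0.77 | 0.65 |
| 0.8 | 1.00 | 0.98 | 0.96 | 0.93 | 0.84 | 0.75 |
| 1.0 | 1.00 | 0.99 | 0.97 | 0.95 | 0.88 | 0.82 |
| 1.2 | 1.00 | 0.99 | 0.98 | 0.96 | 0.91 | 0.85 |

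As a check, the population value under this model is (exp(s_b²) − 1) / (exp(s_b² + s_e²) − 1). For s_b = 0.8 and s_e = 0.15 it is 0.8965 / 0.9396 = 0.954, and for s_b = 0.6 and s_e = 0.4 it is 0.4333 / 0.6820 = 0.635. Both are close to the simulated medians. Over the same grid at k = 2, median CCC is 0.38 to 0.73.

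**4. Random disagreement does lower r.** At s_b = 0.8 and s_e of 0.5, 0.7 and 1.0, median r is 0.64, 0.45 and 0.23.

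**5. Percent change.** Let the second reader's area be k_b times the first's at baseline and k_f times at follow-up. If the first reader's follow-up-to-baseline ratio is R, the percent changes are 100(R − 1) and 100((k_f / k_b)R − 1). When k_f = k_b they are identical. When k_f / k_b = 1.5 and R = 0.5, they are −50% and 100(0.75 − 1) = −25%, a gap of 25 percentage points. By step 1, r at screening does not depend on k_b and r at nadir does not depend on k_f, so neither planned coefficient would register the gap.

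**6. What paired limits would show.** The log ratio of the readers has SD √2 × 0.15 = 0.212 in the setting of step 2. The 95% ratio limits are k·exp(±1.96 × 0.212), that is 0.66 to 1.52 at k = 1 and 1.32 to 3.03 at k = 2.

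**The case against.** Much of the opposing case stands.

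- A reader might infer that r cannot reveal disagreement at all, or that it would sit in a narrow high band such as 0.94 to 0.99 whatever the radiologists did. The documents support neither. Step 4 shows that r falls with random disagreement, and any such band depends on the assumed spread and noise.
- A reader might infer that the SAP judges reader agreement by r. It does not say so. The item is called a correlation, sets no criterion and draws no conclusion. Where the SAP means agreement it plans concordance rates, as in 9.4 and 10.2.7.
- A uniform twofold difference would be visible in the by-reader absolute SPD summaries and the listings. It would cancel in percent change and hence in the waterfall plots. The SPD response thresholds in SAP Table 3 are relative too.
- A reader might infer that ORR, PFS or DoR is at risk. Those endpoints use the central response assessment and do not draw on item 3. The review process is left to the IRC Charter, which is not among the documents, so any handling of reader agreement there is unknown.
- The SAP does not say whether nadir is set separately for each reader or at a common scan. That the nadir coefficient pairs different images is possible but not established.

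The gap that remains is narrower. Side-by-side summaries describe each reader separately and give no within-patient difference or limits, and listings leave that calculation to whoever reads the report. A bias that changes between baseline and follow-up does alter percent change, and no planned statistic measures it as a paired difference.

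**Conclusion.** The point holds as an optional improvement to an exploratory item. That r is blind to a constant or proportional reader difference is exact and rests on no assumption. The sizes are illustrative: r of about 0.65 to 1.00, and CCC of 0.38 to 0.73 at a twofold ratio, rest on lognormal areas, between-patient log-SD of 0.6 to 1.2 and reader log-SD of 0 to 0.4. The 25-point gap in percent change is a worked example with an assumed 1.5-fold shift at follow-up only; nothing in the documents suggests that the readers differ in this way. Primary and secondary endpoints are unaffected.

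**What to change.** In SAP 11.3 item 3, replace Pearson's r or supplement it with:

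- **Screening SPD:** Bland-Altman ratio limits of agreement on log SPD, plus an absolute-agreement ICC or Lin's CCC with 95% confidence interval, where SPD is positive. Lead with the limits, because CCC also depends on the between-patient spread.
- **Percent change from baseline:** Bland-Altman limits on the paired reader difference in percentage points, at a common post-baseline visit and for best percent change. This needs no logarithm, so areas that shrink to zero are handled directly. A log(x + 1) transformation should not be used: applied to area it depends on the unit, and applied to percent change it is undefined at complete shrinkage.

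The cost is a short SAP edit and a few extra lines of output on data already held. The reported figure may look less favourable than r.
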